2.4.3 Extent of investigational medicinal product exposure and compliance

The extent of IMP exposure and compliance will be assessed and summarized by the treatment category and overall on the safety population (Section 2.3.2).

2.4.3.1 Extent of investigational medicinal product exposure

The extent of IMP exposure will be assessed by the duration of IMP exposure in LTS12551 study.

Duration of investigational product exposure is defined as: the last IMP dose date in LTS12551 study – the first IMP dose date in LTS12551 study + 14 days, regardless of unplanned intermittent discontinuations (see Section 2.5.3 for calculation in case of missing or incomplete data).

Duration of IMP exposure will be summarized descriptively as a quantitative variable (number, mean, SD, median, minimum, and maximum). In addition, duration of treatment exposure will also be summarized categorically by counts and percentages for each of the following categories and cumulatively according to these categories (the categories exceeding Week 48 may apply to only the patients on the 96-week treatment period who signed the informed consent form before the approval of protocol amendment 4):

 \leq 4 week

- > 4 and \leq 12 weeks
- > 12 and ≤ 24 weeks
- > 24 and ≤ 48 weeks
- > 48 and \leq 72 weeks
- > 72 and \leq 96 weeks
- >96 weeks

Additionally, the cumulative duration of treatment exposure, will be provided in patient years by treatment category and overall (see Section 2.3.2).

Number and percentage of patients will be summarized by total number of injections they received during the LTS12551 study. The number and percentage of patients who receive injection will be summarized by type of administrator (site staff, patient or non-professional care giver, professional care giver at home), by dosing week, and maybe by IMP packaging way (vial or pre-filled syringe).

2.4.3.2 Compliance

A given IMP administration will be considered noncompliant if the patient did not take the planned dose of treatment as required by the protocol. No imputation will be made for patients with missing or incomplete data. An administration is considered compliant if an injection is performed, regardless the actual amount of solution injected.

The loading dose will be considered as two administrations, and the administration of loading dose will be considered compliant if both the two injections are performed. The loading dose on Day 1 of LTS12551 is applied to patients from DRI12544 only, and is not applicable to patients from EFC13579, EFC13691 or PDY14192.

Percentage of compliance for a patient will be defined as the number of administrations that the patient was compliant divided by the total number of administrations that the patient was planned to take during the treatment epoch defined in Section 2.1.4.

Treatment compliance percentages will be summarized descriptively as quantitative variables (number, mean, SD, median, minimum, and maximum). The percentage of patients whose compliance is < 80% will be summarized.

Cases of overdose (at least twice the dose during an interval of less than 11 days) will constitute serious adverse events and will be listed as such. More generally, dosing irregularities will be listed in Section 2.2.1.

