
Route of administration
	
SC.

[figure not shown]
Dose regimen	
Eligible patients will receive dupilumab 300 mg (SC) q2w, of open-label treatment for 48 weeks (1 year) for patients enrolled after approval of Amendment 04 or 96 weeks (2 years) for patients enrolled prior to Amendment 04 approval.
 
Note: Enrollment from Study DRI12544 is complete; all patients were given a 600 mg loading dose on Day 1.

Noninvestigational medicinal product(s) (if applicable)
 
Formulation
	
Asthma background controller therapy: Inhaled corticosteroid, in combination with a second controller. Patients requiring a third controller medication are allowed (eg, long-acting beta-agonist [LABA], leukotriene receptor antagonist [LTRA], methylxanthines, etc); OCS only for those patients from EFC13691.
 
Asthma reliever medication Patients may receive salbutamol/albuterol hydrofluoroalkane pressurized metered dose inhalers (MDI) or levosalbutamol/levalbuterol hydrofluoroalkane pressurized MDI as reliever medication (as needed) during the study. Nebulizer solutions with either albuterol/salbutamol or levalbuterol/levosalbutamol may be used as an alternative delivery method.

Route(s) of administration	
Oral inhalation, nebulizers: ICS, ICS combination, albuterol/salbutamol or levalbuterol/levosalbutamol; for other background controllers according to the label.

Dose regimen	
Inhaled corticosteroid (medium or high dose); albuterol/salbutamol or levalbuterol/levosalbutamol (as needed); other background controllers according to the label.

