8.1.3 Dose schedule

The IMP is administered every 14±3 days (q2w). The consecutive doses of the IMP must be separated by ≥11 days to avoid an overdose. Reminder: Patients will be monitored for any signs or symptoms of hypersensitivity reactions for a minimum of 30 minutes after IMP injection.

At the Enrollment (Combined V1/V2) Visit, the Investigator or delegate will train the patient (and/or caregiver[s]) how to prepare and inject IMP for the first injection or if the patient is already self-injecting (in the parent study), the Investigator or delegate will supervise the self-injection.

For subsequent doses, which are not given at the study site, specific pages will be provided to the patients to record information related to the injections. The pages will be kept as source data in the patient's study file.

If the patient (or caregiver) is unable or unwilling to administer IMP, arrangements must be made for qualified site personnel and/or healthcare professionals (eg, visiting nurse service) to administer IMP for the doses that are not scheduled to be given at the study site.

If the study visit is not performed at the study site as scheduled, the dose will be administered by the patient and/or their caregiver/healthcare professional, or arrangements must be made for a visit to the site to administer the IMP.

When IMP is administered at home, the patients must be advised by the site staff, to self-monitor for at least 30 minutes after administration for potential signs and symptoms that may suggest a hypersensitivity reaction.

Subcutaneous injection sites should be alternated between the 4 quadrants of the abdomen (avoiding navel and waist areas), the upper thighs, or upper arms (lateral side), so that the same site is not injected twice consecutively. Injection in the upper arms could be done only by a trained person (parent/caregiver trained by Investigator or delegate) or health care professional but not the patient themselves. For each injection, the anatomic site of administration will be recorded in the electronic case report form (e-CRF) and, as applicable, the home dosing diary.

Detailed instructions for transport, storage, preparation, and administration of IMP are provided to the patient.

Patients will complete a home dosing diary to document compliance with self-injection (or parent or caregiver injection) of IMP.

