10.4.1.2 Serious adverse event

An SAE is any untoward medical occurrence that at any dose:

- Results in death, or
- Is life-threatening, or
Note: The term “life-threatening” in the definition of “serious” refers to an event in which the patient was at risk of death at the time of the event; it does not refer to an event which hypothetically might have caused death if it were more severe.
- Requires inpatient hospitalization or prolongation of existing hospitalization, or
- Results in persistent or significant disability/incapacity, or
- Is a congenital anomaly/birth defect, or
- Is a medically important event.

Medical and scientific judgment should be exercised in deciding whether expedited reporting is appropriate in other situations, such as important medical events that may not be immediately life-threatening or result in death or hospitalization, but may jeopardize the patient or may require medical or surgical intervention (ie, specific measures or corrective treatment) to prevent one of the other outcomes listed in the definition above.

Note: The following list of medically important events is intended to serve as a guideline for determining which condition has to be considered as a medically important event. The list is not intended to be exhaustive:

- Intensive treatment in an emergency room or at home for:
 - Allergic bronchospasm, Anaphylaxis. See [Appendix H](#) for the Definition of Anaphylaxis.
 - Blood dyscrasias (ie, agranulocytosis, aplastic anemia, bone marrow aplasia, myelodysplasia, pancytopenia, etc).
 - Convulsions (seizures, epilepsy, epileptic fit, absence, etc).
- Development of drug dependence or drug abuse.
- ALT >3 x ULN + total bilirubin >2 x ULN or ALT increase >10 x ULN.
- Suicide attempt or any event suggestive of suicidality.
- Syncope, loss of consciousness (except if documented as a consequence of blood sampling).

- Bullous cutaneous eruptions.
- Cancers diagnosed during the study or aggravated during the study (only if judged unusual/significant by the Investigators in oncology studies).
- Chronic neurodegenerative diseases (newly diagnosed) or aggravated during the study (only if judged unusual/significant by the Investigators in studies assessing specifically the effect of a study drug on these diseases).

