10.4.1.3 Adverse event of special interest

An AESI is an AE (serious or non-serious) of scientific and medical concern specific to the Sponsor's product or program, for which ongoing monitoring and immediate notification by the Investigator to the Sponsor is required. Such events may require further investigation in order to characterize and understand them. AESIs may be added or removed during a study by protocol amendment.

For these AESIs, the Sponsor will be informed immediately (ie, within 24 hours), per SAE notification described in [Section 10.4.3](#), even if not fulfilling a seriousness criterion, using the corresponding pages/screens in the e-CRF.

- Anaphylactic reactions or systemic allergic reactions that are related to IMP and require treatment (see [Appendix H](#) for Definition of Anaphylaxis).
- Severe injection site reactions that last longer than 24 hours.
- Any infection meeting at least one of the following criteria (see [Section 10.6.3](#)):
 - Any serious infection (SAE).
 - Requires parenteral (intravenous, intramuscular, SC) antimicrobial therapy.
 - Requires oral antimicrobial therapy for longer than 2 weeks.
 - Is a parasitic infection.
 - Is an opportunistic infection (see [Appendix I](#)).

Note: Antimicrobial therapy refers to antibiotic, antiviral, and antifungal agents.

- Significant ALT elevation:
 - ALT >5 x the ULN in patients with baseline ALT ≤2 x ULN; or
 - ALT >8 x ULN if baseline ALT >2 x ULN.
- Pregnancy:
 - Pregnancy occurring in a female patient entered in the clinical trial or in a female partner of a male patient entered in the clinical trial. It will be qualified as an SAE only if it fulfills one of the seriousness criteria (see [Section 10.4.1.2](#)).
 - In the event of pregnancy in a female participant, IMP should be discontinued.
 - Follow-up of the pregnancy in a female participant or in a female partner of a male participant is mandatory until the outcome has been determined (see [Section 9.2.1.4.1](#)).

- Symptomatic overdose with IMP/Non-IMP:
 - An accidental or intentional overdose with the IMP/Non-IMP is an event suspected by the Investigator or spontaneously notified by the patient and defined as at least twice the planned dose during an interval of less than 11 days. The circumstances (ie, accidental or intentional) should be clearly specified in the verbatim and symptoms, if any, entered on separate AE forms.

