10.4.5 Guidelines for management of specific laboratory abnormalities

Decision trees for the management of certain laboratory abnormalities by sanofi are provided in [Appendix D](#).

The following laboratory abnormalities should be monitored, documented, and managed according to the related flow chart in protocol appendices:

- Neutropenia;
- Thrombocytopenia;
- Increase in ALT;
- Acute renal insufficiency;
- Suspicion of rhabdomyolysis.

In addition, on treatment eosinophil counts >3000 cells/ μ L (3.0 giga/L) are to be reported as AEs.

NOTE: Increase in ALT is considered as an AESI (see [Section 10.4.1.3](#)).

Appropriate reporting according to categories will appear in the CRF instructions/completion guide.

Table 6 - Summary of adverse event reporting instructions

EVENT CATEGORY	REPORTING TIMEFRAME	SPECIFIC EVENTS IN THIS CATEGORY	CASE REPORT FORM COMPLETION		
			AE form	Safety Complementary Form	Other specific forms
AE (non-SAE, non-AESI)	Routine	Any AE that is not SAE or AESI	Yes	No	No
SAE (non-AESI or AESI)	Expedited (within 24 hours)	Any AE meeting seriousness criterion per Section 10.4.1.2	Yes	Yes	No
Adverse Event of Special Interest	Expedited (within 24 hours)	As per Section 10.4.1.3	Yes	Yes	No

Abbreviations: AE = Adverse event; AESI = Adverse event of special interest; SAE = Serious adverse event

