Parasitic infection	The Infection Type 'Parasitic' was checked on the eCRF page "Infection Defined as AESI Complementary Form"
Opportunistic infection	The Infection Type 'Opportunistic' was checked on the eCRF page "Infection Defined as AESI Complementary Form"

Table 3 -	Criteria for	r adverse event	s of specia	l interest and	l other selec	ted AE grounings
			s of specia	i multicst and	i other serve	icu All groupings

AE Grouping	Criteria
Drug-related hepatic disorder	Drug-related hepatic disorders - Comprehensive search narrow SMQ (20000006)
Pregnancy	Primary SOC = 'Pregnancy, puerperium and perinatal conditions', or PT in (Aborted pregnancy, False negative pregnancy test, Pregnancy test positive, Pregnancy test urine positive, Ectopic pregnancy termination)
Symptomatic overdose with IMP	The question "Is the event a Symptomatic Overdose with IMP?" is answered "Yes" on the eCRF page "Adverse Event"
Symptomatic overdose with non-IMP	The question "Is the event a Symptomatic Overdose with non-IMP?" is answered "Yes" on the eCRF page "Adverse Event"
Other selected AE grouping	
Injection site reaction	HLT = 'Injection site reaction'
Malignancy	Sub-SMQ (20000091) – Malignant or unspecified tumors
Suicidal behavior	PT in (Completed suicide, Suicidal ideation, Depression suicidal, Suicidal behavior, Suicide attempt)
Partner pregnancy	PT in (Pregnancy of partner, Miscarriage of partner)
Conjunctivitis (narrow)	PT in (Conjunctivitis, Conjunctivitis allergic, Conjunctivitis bacterial, Conjunctivitis viral, Atopic keratoconjunctivitis)
Conjunctivitis (broad)	PT in (Conjunctivitis, Conjunctivitis allergic, Conjunctivitis bacterial, Conjunctivitis viral, Atopic keratoconjunctivitis, Blepharitis, Dry eye, Eye irritation, Eye pruritus, Lacrimation increased, Eye discharge, Foreign body sensation in eyes, Photophobia, Xerophthalmia, Ocular hyperaemia, Conjunctival hyperaemia)
Hypereosinophilia	HLT = 'Eosinophilic disorders' or PT = 'Eosinophil count increased'

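### SAP 2.4.3.2 classes every IMP overdose as a serious adverse event, contrary to the protocol's seriousness criteria and reporting timelines

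*SAP*

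**What the plan says.** SAP 2.4.3.2, on compliance with study drug, says: "Cases of overdose (at least twice the dose during an interval of less than 11 days) will constitute serious adverse events". It adds that the cases will be listed accordingly.

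The protocol deals with the same subject in several places:

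- **10.4.1.2** opens its definition with "An SAE is any untoward medical occurrence that at any dose" and then gives the criteria: death, threat to life, hospitalization, disability, congenital anomaly, or medical importance. Neither the criteria nor the examples of medically important events name overdose.
- **10.4.1.3** makes symptomatic overdose an AESI. IMP overdose is "defined as at least twice the planned dose during an interval of less than 11 days". The same section says an AESI can be serious or non-serious.
- **Table 5 (10.4.2)** sets 24 hours for serious events, 24 hours for symptomatic overdose, and routine reporting for asymptomatic overdose.
- **Table 6 (10.4.5)** describes the serious-event category as "Any AE meeting seriousness criterion per Section 10.4.1.2".
- **8.1.3** states: "The consecutive doses of the IMP must be separated by ≥11 days to avoid an overdose".

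**The concern.** The SAP assigns seriousness by category, whereas the protocol assigns it event by event against criteria. An overdose without symptoms or serious outcome is therefore non-serious when the site reports it and serious in the SAP's listing.

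Long-term safety is the primary objective, so serious-event outputs will be read closely. SAP Section 3 also has all planned analyses run for the asthma submission report, so the inconsistency could reach that report. A reader who finds overdoses listed as serious but absent from the serious-event tables cannot tell whether the listing is mislabelled or the tables are incomplete.

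**Working it through.** The plan gives no figure to reproduce, and no test, power or event count is involved. The check compares the rules case by case. I read the SAP sentence as covering IMP overdose only, because it sits in the IMP compliance section and uses the 11-day window. The protocol defines non-IMP overdose separately.

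| Case | Protocol | SAP 2.4.3.2 | Result |
|---|---|---|---|
| (a) No symptoms, no seriousness criterion met | Not serious; routine reporting (Table 5) | Serious | Direct conflict |
| (b) Symptoms, no seriousness criterion met | Non-serious AESI; 24 hours (10.4.1.3, Table 5) | Serious | Conflict on seriousness |
| (c) A 10.4.1.2 criterion met | Serious; 24 hours | Serious | Agreement |

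Case (a) is the clearest. If every overdose were serious, every overdose would be due within 24 hours, and Table 5 could not give the asymptomatic ones a routine timeline. Table 6 points the same way: it allows routine reporting only for events that are neither serious nor AESIs.

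**Reach of case (a).** Doses are due every 14 ± 3 days, so the shortest permitted gap is 14 − 3 = 11 days. Two 300 mg injections 10 days apart give 300 + 300 = 600 mg, and 600 / 300 = 2 times the planned dose in under 11 days. That meets the overdose definition and agrees with the stated purpose of the 11-day minimum in 8.1.3. A gap one day short, with no symptoms, would be listed as a serious adverse event.

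**Effect on outputs.** SAP 2.1.4 bases the safety analysis on reported adverse events. Section 2.4.5.1 plans treatment-emergent serious adverse event tables, and none of them is defined from the overdose sentence. Sites report under the protocol, so cases (a) and (b) would appear as serious in the overdose listing and not in those tables.

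**The case against.** **The sentence is narrow.** It promises only a listing, sits in the compliance section, and does not alter what sites report. This stands and limits the size of the problem. A reader might infer that the serious-event tables will be inflated. The documents do not say so; it would happen only if the rule were carried into those tables.

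**Medical importance is open-ended.** Protocol 10.4.1.2 says its list of examples is not exhaustive, so an overdose can be judged serious. That is true of an individual event and belongs to case (c). It gives no basis for a blanket rule.

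**SAP Table 3.** A reader might see a contradiction here too, since Table 3 picks up IMP overdose only where the e-CRF question "Is the event a Symptomatic Overdose with IMP" is answered yes. But Table 3 is an AESI search list that does not address seriousness. The protocol allows an event to be both an AESI and serious, so the two entries can coexist.

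**The loading dose.** The SAP sentence omits the protocol's word planned. For patients from DRI12544, the protocol synopsis notes that "all patients were given a 600 mg loading dose on Day 1", and SAP 2.4.3.2 says "The loading dose will be considered as two administrations". A literal reader might conclude that each loading dose (600 / 300 = 2) is an overdose. That reading is strained. The same SAP section judges administrations against the planned dose and treats the loading dose as compliant when both injections are given.

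**Conclusion.** SAP 2.4.3.2 is wrong as written. It conflicts with protocol 10.4.1.2, 10.4.1.3, Table 5 and Table 6 for any IMP overdose that meets no seriousness criterion, including symptom-free dosing-interval deviations. The passages must be reconciled.

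The consequence is a listing that labels non-serious events as serious and does not agree with the serious-event tables. The primary endpoint, any treatment-emergent adverse event, is unaffected, because relabelling a reported event as serious does not change whether the patient has one. This assumes that the sentence relabels reported events and does not create new adverse event records, as SAP 2.1.4 implies.

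The number of cases cannot be estimated. Neither document gives the share of dosing intervals shorter than 11 days, so any projected count would rest on an invented rate.

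**What to change.** Reconcile the SAP sentence with the protocol. For example, replace it with:

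> IMP overdoses, as defined in protocol 10.4.1.3, will be listed. An overdose is counted as a serious adverse event only if it meets a seriousness criterion in protocol 10.4.1.2. Symptomatic overdose is summarized as an AESI (Table 3).

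Citing the protocol definition also restores the word planned and removes any doubt about the loading dose. The cost is one sentence in the SAP and a matching label on the overdose listing. No data collection, table definition or site instruction changes.

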2.4.4 Analyses of efficacy endpoints

There will be no confirmatory analysis for the efficacy variables. All analyses will be done descriptively on the safety population in observed case, as appropriate. The baseline value for efficacy parameters is the original baselines from the parent studies.

For severe exacerbation events, the number of patients with one or more severe exacerbation events (number and qualitative variable: Yes/No), number of severe exacerbation events (qualitative variable: 0, 1, 2, 3, \geq 4), total number of severe exacerbation events, total patient-years, unadjusted annualized severe exacerbation event rate, and individual patient annualized severe exacerbation event rate (number, mean, SD, median, minimum, maximum) will be presented by the treatment category and overall (see Section 2.3.2) during the treatment period. Number and annualized rate will also be analyzed for severe exacerbation with use of systemic corticosteroids for \geq 3 days only, and that with hospitalization or with emergency room visit only. The mean duration of a severe exacerbation will also be summarized.

For the continuous efficacy variables listed in Section 2.1.3, descriptive statistics (mean, SD, median, minimum and maximum) will be presented for the parameter and its change from baseline over visits and by the treatment category and overall (see Section 2.3.2). In addition, figure of mean change from baseline (with corresponding standard error) will be presented for the continuous efficacy parameter over visits and by the treatment category and overall (see Section 2.3.2).

For the categorical efficacy variables listed in Section 2.1.3, the number and percentage will be presented over time for all patients who have data available at that time point by the treatment category and overall (see Section 2.3.2).

In addition, particularly for the patients coming from the EFC13691 study, the descriptive statistics (mean, SD, median, minimum and maximum) for the percentage change from baseline in oral corticosteroids (OCS) dose will be presented over time by the treatment category and overall (see Section 2.3.2); and, the proportion of patients achieving a reduction of 50% or greater in their OCS dose compared with the original baseline in parent study, and the proportion of patients whose background OCS are completely tapered off will be presented over time by the treatment category and overall (see Section 2.3.2).

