6 STUDY DESIGN

6.1 DESCRIPTION OF THE PROTOCOL

Multinational, multicenter, open-label, extension study evaluating dupilumab 300 mg (SC) q2w for 1-year (48 weeks) or 2-year (96 weeks) treatment duration. Patients enrolled prior to Amendment 04 approval will continue to participate in the 2-year treatment duration; patients enrolled after Amendment 04 approval will participate in the 1-year treatment duration.

At enrollment, patients will be on medium or high dose of ICS and at least one other asthma controller medication, as maintained during the parent study in which they participated (including asthma background controller therapy with OCS only for patients from Study EFC13691).

For a schematic study design please see [Section 1.1](#).

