1 OVERVIEW AND INVESTIGATIONAL PLAN

1.1 STUDY DESIGN AND RANDOMIZATION

LTS12551 is a multinational, multicenter, 1-year (48 weeks) or 2-year (96 weeks) single arm extension study to evaluate the long-term safety and tolerability of dupilumab in patients with asthma, who completed the treatment and follow-up period in the DRI12544 study, or who completed the treatment period in the EFC13579, EFC13691 or PDY14192 studies.

In the LTS12551 study, dupilumab 300 mg is administered subcutaneously (SC) every 2 weeks (q2w), as an add-on therapy to a variety of allowable combinations between inhaled corticosteroid (ICS) and other controller medications as maintained during the parent study, including the oral corticosteroids (OCS) medication for the patients from the EFC13691 study. The LTS12551 consists of three periods:

- Screening Period (0-3 weeks, if applicable)
- Treatment Period (48 weeks open-label period for the patients enrolled after the protocol amendment 4, or 96 weeks open-label period for the patients enrolled before the protocol amendment 4)
- Post-treatment Period (12 weeks, dupilumab-free follow-up period)

The 4 parent studies are described briefly as follows:

DRI12544: A phase 2b, randomized, double-blind, placebo-controlled, dose ranging, parallel group study comparing different doses and regimens of dupilumab SC for 24 weeks in patients with moderate to severe, uncontrolled asthma. Patients were randomized in ratio of 1:1:1:1:1 into 5 arms, dupilumab 200 mg every 4 weeks (q4w), dupilumab 300 mg q4w, dupilumab 200 mg q2w, dupilumab 300 mg q2w, and placebo. Patients were allowed to administer moderate- or high-dose inhaled corticosteroid (ICS) in combination with long-acting beta agonist (LABA) as follows: mometasone furoate / formoterol, budesonide / formoterol, and fluticasone propionate / salmeterol in the treatment period, and continued with the stable dosage of controller medications in the 16-week post-treatment follow-up period. There were 776 patients enrolled in DRI12544.

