1.6 STATISTICAL MODIFICATIONS MADE IN THE STATISTICAL ANALYSIS PLAN

This statistical analysis plan (SAP) version 3.0 is based on the LTS12551 amended protocol 2 (protocol amendment 4) dated October 31st, 2016, and is the third version of SAP for LTS12551.

SAP version number	Date approved	Rationale	Description of statistical changes
2	23-Nov-2016	Protocol amendment 4 shortens the open-label treatment period to 48 weeks.	The open-label treatment duration is amended to 48 weeks for patients providing consents after the implementation of the protocol amendment 4.
2	23-Nov-2016	Protocol amendment 4 drops the electronic diary, PEF meter, EQ-5D-3L, serum immunoglobulins, and serum total IgE for all the patients in LTS12551 study. Before the protocol amendment 4 becomes effective, the patients from	The analyses for AM/PM PEF, AM/PM asthma symptom score, number of reliever uses, number of nocturnal awakenings, EQ-5D-3L score, serum immunoglobulins and serum total IgE in LTS12551 study will be restricted to the patients from the DRI12544 study and performed to the data observed up

SAP			
version	Date		
number	approved	Rationale	Description of statistical changes
		DRI12544 study have data collection for the aforementioned endpoints for more than one year, while only a few of patients from EFC13579, EFC13691 or PDY14192 studies have limited amount of data collected for those endpoints.	to the end of their collection. The compliance for background controller medications will be calculated using the data observed up to the end of the electronic diary collection.
2	23-Nov-2016	Protocol amendment 4 adds three efficacy endpoints linked to the prescribed OCS dose for the patients from the EFC13691 study only. They are the percentage change from baseline in the OCS dose, the proportion of patients achieving a reduction of 50% or greater in the OCS dose compared with the baseline, and the proportion of patients whose background OCS are completely tapered off. The baseline OCS dose is defined as the original baseline value of the parent study.	The proportion of patients whose background OCS are completely tapered off and its analysis have been added to this version of SAP, and the other two endpoints linked to the OCS dose and their corresponding analyses have already existed in the SAP 1.0.

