2.3.2 Safety population

The safety population is defined as the patients who have actually received at least 1 dose or part of a dose of the IMP in LTS12551.

Enrolled patients for whom it is unclear whether they took the IMP or not will be included in the safety population as enrolled.

The treatment category "Placebo/Dupilumab" is defined as the patients who have been in the actual placebo arms of the parent studies and exposed to Dupilumab in LTS12551. The treatment category "Dupilumab/Dupilumab" is defined as the patients who have been in the actual Dupilumab arms of the parent studies and exposed to Dupilumab in LTS12551.

For the OCS dependent patients, results of each planned analysis will be presented by "Placebo/Dupilumab", "Dupilumab/Dupilumab" and "All".

For the non-OCS dependent patients, results of each planned analysis will be presented by the parent study and "All", and further by "Placebo/Dupilumab" and "Dupilumab/Dupilumab" within each parent study.

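### After Week 48 the pooled non-OCS, EFC13579 and EFC13691 by-visit spirometry and OCS-dose displays cover only patients on the 96-week plan, so a step there need not be a change in effect

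*SAP*

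**What the plan says.** Protocol 6.1 sets treatment length by enrolment date: "Patients enrolled prior to Amendment 04 approval will continue to participate in the 2-year treatment duration", while "patients enrolled after Amendment 04 approval will participate in the 1-year treatment duration". SAP 1.1 repeats this, with a "48 weeks open-label period for the patients enrolled after the protocol amendment 4".

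For efficacy, SAP 2.4.4 states: "All analyses will be done descriptively on the safety population in observed case, as appropriate". For continuous variables, "descriptive statistics (mean, SD, median, minimum and maximum) will be presented for the parameter and its change from baseline over visits", and a "figure of mean change from baseline (with corresponding standard error) will be presented for the continuous efficacy parameter over visits". The OCS-dose summaries for EFC13691 patients are also presented over time.

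The layout is in SAP 2.3.2. "For the non-OCS dependent patients, results of each planned analysis will be presented by the parent study and" an 'All' group, then by prior placebo or dupilumab within each study. EFC13691 patients are shown separately, by prior arm and 'All'. Neither section splits by planned duration or cuts a display at Week 48.

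SAP 2.1.3.2 marks the Week 72 and Week 84 spirometry visits as applying only where relevant. SAP 2.4.3.1 notes that exposure categories beyond Week 48 may concern only the 96-week patients. The efficacy section has no such note.

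**The concern.** In an observed-case summary each visit's mean is taken over whoever has a value. Up to Week 48 that includes both planned-duration cohorts. Afterwards the 48-week cohort has no on-treatment visits, so the mean is taken over the remaining subset, selected by enrolment date. The curve is drawn as one line across that change.

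Long-term efficacy is a secondary objective, and no model or test accompanies these displays. A reader who wants to know whether lung function or OCS reduction holds in the second year has only the plotted means. If patients on the 96-week plan differ on average from the others, the line steps between Week 48 and the next visit even if every patient is stable. A true decline can be hidden in the same way.

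**Working it through.** **The plan's own size figure.** SAP 1.1 gives parent-study sizes of 776 (DRI12544), 1902 (EFC13579), 210 (EFC13691) and 42 (PDY14192). Their sum is 2930, which agrees with the maximum in SAP 1.3. There is no power or alpha figure to reproduce, because all efficacy analysis is descriptive.

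**Visits affected.** On-treatment post-baseline spirometry on the 96-week plan falls at Weeks 2, 4, 8, 12, 24, 48, 72, 84 and 96 (SAP 2.1.3.2). Three of the nine come after Week 48. Prescribed OCS dose also has a Week 60 window (SAP 2.5.4, Table 6).

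**Displays affected.**
- Affected: FEV1, percent predicted FEV1, FVC and FEF 25-75% in the non-OCS 'All', EFC13579 and EFC13691 displays, and the EFC13691 OCS-dose summaries.
- Not affected: the DRI12544 curve. Enrolment from that study was complete (Protocol 6.2.1), so all its patients are on 96 weeks.
- Not affected: ACQ-5 and AQLQ, which have no Table 6 window after Week 48.
- Not affected: the diary endpoints and EQ-5D-3L, which are analysed in DRI12544 patients only (SAP 2.1.3.5 and 2.1.3.6).

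**Shift in the non-OCS 'All' curve.** Let f be the share of EFC13579 and PDY14192 patients on the 96-week plan; the documents do not give it. Assume parent-study sizes, equal rollover, no dropout, and the same mean for early and late enrollees within a study. Let D be the gap between the DRI12544 mean change and that of the other studies.

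- DRI12544 share to Week 48: 776/(776 + 1902 + 42) = 776/2720 = 0.285.
- DRI12544 share after Week 48: s = 776/(776 + 1944f).
- Shift with no patient changing: (s − 0.285) × D.

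| f (assumed) | n after Week 48 | s | Shift | D = 0.05 L | D = 0.10 L | D = 0.20 L |
|---|---|---|---|---|---|---|
| 0.05 | 873 | 0.889 | 0.60 D | 0.030 L | 0.060 L | 0.121 L |
| 0.20 | 1165 | 0.666 | 0.38 D | 0.019 L | 0.038 L | 0.076 L |
| 0.50 | 1748 | 0.444 | 0.16 D | 0.008 L | 0.016 L | 0.032 L |

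The values of D are assumed.

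**Unequal rollover.** The protocol synopsis expects about 2206 patients. If all 776 DRI12544 patients are among them, the starting share is 776/2206 = 35% (no EFC13691 patients in the total) to 776/(2206 − 210) = 776/1996 = 39% (all 210 in it). The other non-OCS patients then number 1430 or 1220. For f = 0.05, 0.20 and 0.50 the shift is 0.56, 0.38 and 0.17 times D from the first start, and 0.54, 0.37 and 0.17 times D from the second. The result is not sensitive to this assumption.

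**Shift inside an EFC curve.** If early and late enrollees of one study differ by G, the curve moves by (1 − f) × G after Week 48, here with f the 96-week share within that study: 0.95 G, 0.80 G or 0.50 G for the same three values. With equal SD, the standard error grows by 1/√f, that is 4.5-, 2.2- or 1.4-fold. EFC13691 would keep about 10, 42 or 105 of 210 patients.

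**Window overlap.** A 1-year patient's end-of-study visit at Week 60 targets day 60 × 7 + 1 = 421, or days 414 to 428 with the one-week visit window. It belongs to the EOS row of Table 6, which starts the day after treatment ends. Day 421 also lies in the Week 72 spirometry window (421 to 546) and the Week 60 OCS window (379 to 462). The rule of taking the value closest to target works within a window and does not choose between rows. Post-treatment values from 48-week patients could therefore enter on-treatment points at which they have no other value.

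**The case against.** The strongest reply is that the layout already deals with this. SAP 1.6 records that version 3 changed all outputs to avoid between-study confounding. Results appear by parent study, and the DRI12544 spirometry curve has no cohort break, so a clean second-year display exists. That stands for DRI12544. It does not stand for 'All', which brings back the between-study difference once the mix changes, or for EFC13579 and EFC13691, where the break can lie inside the study.

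Second, these are descriptive secondary summaries, and the Amendment 04 rationale in SAP 1.5 expects one year of data to be sufficient. That limits the importance of the point but does not make the later points readable.

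Third, a fall in n would be visible. Protocol 11.4.2 does list the number of patients among the by-visit statistics. The SAP's list for the same tables omits it, and neither document asks for it on the figures.

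A reader might also go further than the documents allow. SAP 1.6 says that "only a few of patients from EFC13579, EFC13691 or PDY14192 studies have limited amount of data collected", which invites the conclusion that the later 'All' points are nearly all DRI12544, with a shift of (1 − 0.285) × D, about 0.07 L for D = 0.10 L. That sentence explains why the diary, EQ-5D-3L and immunoglobulin analyses are restricted to DRI12544. It is not an enrolment count, and the 0.07 L is the limiting case f = 0. Nor is 29% a maximum for the starting DRI12544 share.

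**Conclusion.** The concern holds for the spirometry displays in the non-OCS 'All', EFC13579 and EFC13691 groups and for the EFC13691 OCS-dose summaries over time. Beyond Week 48 these describe a subset fixed by enrolment date, and a step there cannot be read as gain or loss of effect.

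For the 'All' mean the artefact is about 0.16 to 0.60 of any gap between study means, for f from 0.50 down to 0.05. Both f and the gap are assumptions. The artefact disappears only if f = 1 or the groups being mixed have equal means.

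The concern does not extend to efficacy curves in general, and the later points contain a remaining subset rather than new patients. The primary safety endpoint is not involved. It is a modest fault with an inexpensive remedy.

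**What to change.** In SAP 2.4.4:
- End the non-OCS 'All', EFC13579 and EFC13691 by-visit spirometry displays, and the EFC13691 OCS-dose displays, at Week 48.
- Present later visits (Weeks 72 to 96, and Week 60 for OCS dose) only for the cohort planned for 96 weeks, shown from Week 0.
- Print n at each visit in tables and under figures, which restores the item listed in Protocol 11.4.2.
- State that the 96-week display is still observed case and subject to dropout, so it does not follow an identical set of patients throughout.

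In SAP 2.5.4, Table 6, state that post-treatment values go only to the EOS row.

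The cost is a few sentences of SAP text, one extra by-variable in existing programs and a few more figure panels. The DRI12544 displays need no duration split.
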